### 8.3 STATISTICAL METHODS

The data analyses will be based on the analysis populations described above. No imputation for missing data will be performed. The demographic data will be summarized based on study subjects, while eye-related outcomes will be prepared for Cohort 1 and Cohort 2. The eye-related data may also be separated for the

For continuous outcomes, mean, standard deviation, median, minimum, and maximum will be provided. For categorical outcomes, the counts and percentages of eyes with each categorical level of outcomes will be summarized.

#### 8.3.1 SAFETY OUTCOMES

##### 8.3.1.1 *ADVERSE EVENTS AND DEVICE DEFICIENCIES*

Adverse events and device deficiencies will be summarized at each study visit based on the safety population for Cohort 1 and Cohort 2 separately. The number and percentage of eyes reported with the ISO specified 3-month cumulative and persistent adverse events will be calculated for Cohort 1 and Cohort 2 separately.

##### 8.3.1.2 ECC

The within-eye change and percent change in ECC from preoperative to 3 month postoperative visit will be calculated for each eye.

[REDACTED]

[REDACTED]

[REDACTED]

[REDACTED]

### 8.3.2 EFFECTIVENESS OUTCOMES

The effectiveness outcomes will be analyzed based on the Implanted-eye Population and PP Population. The BCDVA will also be summarized based on the Best-case population as suggested by ISO. The analyses for other effectiveness outcomes are exploratory in nature.

#### 8.3.2.1 BCDVA

[REDACTED]

[REDACTED]

[REDACTED] the number and percentage of eyes reaching BCDVA 20/20 or better, 20/25 or better, 20/32 or better, 20/40 or better, and worse than 20/40 at each visit will be prepared for Cohort 1 and Cohort 2 separately.

[REDACTED]

#### 8.3.2.2 UCDVA

[REDACTED] The proportion of eyes with UCDVA of 20/20 or better, 20/25 or better, 20/32 or better, 20/40 or better, and worse than 20/40 at each visit will be summarized for each Cohort at the pre-operative and every postoperative visits.

#### 8.3.2.3 PREDICTION ERROR (PE)

The MRSE prediction error will be calculated for each treated eye as follows:

MRSE PE = Postoperative MRSE adjusted to 6 meters at 3 months – MRSE TRRE (target residual refractive error)

The MRCYL prediction error will be calculated for eyes implanted with HMTIOL as follows:

MRCYL PE = Postoperative MRCYL adjusted to 6 meters at 3 months – MRCYL TRRE (target residual refractive error)

**8.3.2.4        *ROTATION OF IOL MERIDIAN***

The rotation of IOL meridian will be calculated for each eye from Day 0 to every postoperative visit. The descriptive statistics for continuous variables will be used to summarize the rotation angle at each visit for Cohort 1 and Cohort 2 separately. Additionally, the number and percentage of eyes with rotation < 10°, < 20°, and < 30° will be calculated at each visit for Cohort 1 and Cohort 2 separately. [REDACTED]

**8.3.2.5        *REDUCTION IN CYLINDER POWER***

This endpoint is for eyes implanted with HMTIOL.

The reduction in cylinder power will be calculated for each eye as follows:

Cylinder Power Reduction = absolute value of preoperative magnitude of corneal cylinder (K) – absolute postoperative magnitude of MRCYL at the corneal plane.

The percent reduction in cylindrical power will be calculated for eyes with non-zero preoperative corneal cylinder as follows:

Cylinder Power % Reduction = Cylinder Power Reduction/ absolute value of preoperative magnitude of corneal cylinder (K) × 100.

The descriptive statistics for continuous variables will be used to summarize these outcomes at each visit for Cohort 1 and HMTIOL in Cohort 2 separately. [REDACTED]

## 9.0 DATA MANAGEMENT

### 9.1 DATA QUALITY ASSURANCE

All requested information must be entered on the eCRF and confirmable through source documentation. If an item is not available or not applicable, this fact should be clearly indicated.

Data will be entered into a computer database developed specifically for this trial. During the course of the trial, data queries will be generated for data points that are potentially erroneous and require appropriate clarification or correction.

#### 9.1.1 DATA MONITORING

Periodic monitoring (either remote and/or on-site) will take place to ensure data integrity. Study monitoring involves the following elements:

ClarVista personnel, or designee, may meet with investigators prior to the initiation of the study in order to review the adequacy of the subject population, facilities, and equipment with respect to the needs of the study, and to familiarize the investigator and support staff with the study protocol.

ClarVista personnel, or designee, may meet with the investigators at the time enrollment is initiated in order to ensure that subjects are being properly selected, that the methods described in the study protocol are thoroughly understood by the investigator, and that study data are being correctly recorded.

ClarVista personnel, or designee, may visit the clinical site at any time during the course of the study to review and/or collect completed case report forms. Additionally, telephone consultation will occur as necessary during the course of the study to ensure the proper progress and documentation of the study findings.

The study data will be carefully protected, and masking utilized to the extent possible, in order to prevent bias.

#### 9.2 RECORD RETENTION

The investigator shall maintain all subject records for whichever of the following periods is shorter:

- A period of two years after the date on which FDA approves the marketing of the device
- A period of five years after the date on which the results of the study are submitted to the FDA in support of the marketing of the device

OR

- A period equal to the minimum required by the regional authority.

The Investigator / Site must contact ClarVista as provided in the Protocol Contacts page prior to discarding or disposing of any study related supplies or documents. The Sponsor retains the right to have all study documents shipped (at Sponsor's expense) for archival purposes, as an alternative to disposal.

Keratometry	X					X	X
Axial Length	X						
Anterior Chamber Depth	X						
IOL/Toric Power Calculation	X						
Slit Lamp Examination	X			X	X	X	X
Specular Microscopy	X						X
IOP	X			X	X	X	X
Pupil Size	X	X	X				
Surgery / IOL implantation		X	X				
Intraoperative Exchange			X				
				X	X	X	X
IOL Rotational Stability		X	X	X	X	X	X
Dilated Fundus Exam	X						X

 All testing to be conducted on both eyes Will include pregnancy test if applicable If UCDVA is < 20/40, perform Pinhole (PH) vision Measurements via biometry will be utilized for both calculations and data capture To be reviewed and approved by the Sponsor Dilated slit lamp photo submitted to IOL Stability Reading Center

1 TITLE PAGE

Protocol Number: ClarVista CP-00002

Medical Specialty: Surgical

Project Name /Number: NA

Sponsor Name & Address: CLARVISTA MEDICAL, INCORPORATED
[name]
[contact]
[contact]Test Article(s) / Product(s): ClarVista HARMONI® Modular Toric Intraocular Lens
System

Statistical Analysis Plan for Protocol CP-00002

A Prospective, Multi-Center Study to Evaluate the Safety and Performance of the Exchangeable ClarVista HARMONI® Modular Toric Intraocular Lens System for the Treatment of Pre-existing Corneal Astigmatism and Aphakia Following Cataract Surgery

Sponsor

ClarVista Medical, Incorporated

[name]

[name]

[contact]

[contact]

Original Version Date

14 August 2017

Table of Contents

1. Purpose.....	3
2. Scope	3
3. Software	3
4. Design and Objectives	3
5. Statistical Analyses	3
6. Sample Size.....	7
7. Analysis Populations.....	7
8. Interim Analyses.....	8
9. Deviations from the Statistical Analysis Plan	9
10. References.....	9

1. Purpose

This is a feasibility study to evaluate the safety and effectiveness of HARMONI® Modular Toric Intraocular Lens System (HMTIOL) in subjects with primary cataract surgery and subjects with HMTIOL intra-operative optic exchange. There are three objectives in this study -

- To demonstrate the safety and effectiveness of the HMTIOL in subjects with pre-existing corneal astigmatism
- To evaluate endothelial cell loss after an intraoperative optic exchange
- To evaluate refractive outcomes and astigmatism correction with the HMTIOL used in the primary surgery

2. Scope

Analyses described here supersede those described in the Investigational Plan.

3. Software

Statistical analyses will be performed with SAS System Software version 9.4 or above (SAS Institute, Cary, N.C.), R version 3.3 or above (R Core Team, <http://www.R-project.org>), or other validated statistical software package.

4. Design and Objectives

All subjects will be bilaterally implanted based on the amount of pre-existing corneal astigmatism and followed for a period of 3-months post-implantation. The eye with the higher corneal astigmatism will be assigned to Cohort 1 and will undergo cataract surgery receiving HMTIOL. The contralateral eye will be assigned to Cohort 2, undergo cataract surgery, receive a HMTIOL or HMIOL (toric or non-toric optic, respectively), and undergo intraoperative exchange.

5. Statistical Analyses*5.1. General Statistical Methods*

In general, analyses will be provided based on available data.

For continuous measures, descriptive summary statistics will include the number of observations, mean, standard deviation, median, minimum, maximum, as well as the number of eyes with results not reported. For continuous measures analyzed as changes from earlier visits, the 95% confidence interval for change will also be reported. Continuous measures may also be dichotomized or otherwise split into clinically meaningful categories and additionally analyzed as categorical measures.

For categorical measures, the percentage and number of cases for each condition (e.g., 20/40 or better) will be reported. The number of eyes without results will be omitted from the numerator and denominator of such calculations (i.e. no imputation will be performed).

Any calculated p-values will be based on nominal calculations with no adjustment for multiplicity. No imputation for missing data will be performed.

5.2. Baseline Data

Data on enrollment, demographics (gender, race, age, implanted eye), and baseline characteristics (IOL Power, pre-operative MRSE, target MRSE, keratometric cylinder, axial length) will be summarized with descriptive statistics.

5.3. Accountability

Accountability will be based on eyes (not subjects). The number and percentage of eyes available for analysis at each time point will be presented. For eyes not available for analysis, a breakdown will be provided to summarize the following reasons for missing data: subject discontinued, missed study visit but seen later, missed study visit but subject accounted for (i.e., contacted), and lost to follow-up. Eyes for active subjects at a time point, defined as those enrolled but who have not yet reached the corresponding time point, will also be summarized. Accountability as a percentage will be calculated based on the total number available for analysis over the total number of eyes enrolled minus total number discontinued and the total number active.

5.4. Safety Endpoints

- Preservation of BCDVA
- Adverse Events as outlined in ISO 11979-7:2014 Annex B
- Rate of device-related Secondary Surgical Interventions (SSIs), other than initial intraoperative exchange for cohort 2.
- Percent change in Endothelial Cell Count (ECC)
- Device deficiencies

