	
Efficacy Endpoints:
 
 
1. Post op MRCYL for eye implanted with HMTIOL
 
2. Post op MRCYL prediction error for eye implanted with HMTIOL
 
3. Post op SEQ Prediction Error
 
4. UCDVA by study visit
 
5. BCDVA by study visit
 
6. Rotation of IOL meridian from the day of surgery to 3 months             
 
a. Meridian rotation < 10°
 
b. Meridian rotation < 20°
 
c. Meridian rotation < 30°
 
 
 
7. Reduction in cylinder power of eye implanted with HMTIOL             
 
a. Absolute preop magnitude of K (or total corneal cylinder) minus the absolute post op magnitude of MRCYL at the corneal plane
 
 
 
8. Percentage reduction in cylindrical power of eye implanted with HMTIOL             
 
a. Absolute preop magnitude of K (or total corneal cylinder) minus the absolute post op magnitude of MRCYL at the corneal plane expressed as a percentage of the absolute preop magnitude of K (or total corneal cylinder)
 
 
 
 
Safety endpoints:
 
 
9. Percent change in ECC at the 3 Month Visit compared to Preoperative Visit
 
10. Preservation of BCDVA
 
11. SSI (other than interoperative optic exchange in Cohort 2)
 
12. Device deficiency
 
13. AEs rates as compared to ISO 11979-7:2014 Annex B SPE tables
 

	

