### 3.3.3 POST-OPERATIVE VISITS (DAYS 1 – 60)

All subjects implanted with a study lens will be seen for 1 Day, 1 Week, 1 and 3 Month assessments as outlined in Appendix A.

IN ADDITION, the second eye will be implanted during this time period. It is recommended (at the final discretion of the Investigator), to complete this procedure as close to the 1 Week Visit (after first eye cataract extraction) as possible. Since second eye assessments will be completed on the same schedule as the first eye assessments (see Appendix A – Table 1), this will allow the subject further convenience in attending as many post-operative bilateral assessment visits as possible.

The Investigator will carry out the second eye surgical procedure as specified in the Surgical Procedure Manual and the following details will be captured in both Source Documents and eCRFs:

- Date of surgery
- Operative eye
- Cohort 1 or Cohort 2
- Incision location and size
- Ophthalmic Viscoelastic Device (OVD) used
- All medication used pre-, intra-, and post-operatively (ophthalmic and systemic)
- Model, serial number, and diopter of HMIOL implant components
- Toric IOL power and axis orientation (for toric IOL)
- IOL injection device

Once the subject is confirmed stable post-surgery, provide post-operative instructions and discharge.

NOTE: All concomitant medication, AE, and SAE collection must be continued throughout the course of the study. Any outcomes resulting in unacceptable RRE (as determined between Investigator and Subject), can be addressed with spectacles, a contact lens, or surgical correction. Any PO surgical adjustments to outcomes (corneal refractive surgery, lens exchange, etc.) will be carried out as determined to be in the best interest of the subject. The course of treatment will follow the Investigators SOC and be collected as a concomitant procedure.

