#### **6.2.1.4           RELATIONSHIP (CAUSALITY) TO STUDY DEVICE OR STUDY PROTOCOL**

When evaluating AEs, the Investigator must evaluate the relationship of the event to the study device and study protocol, using the following guidelines:

- Not Related: AEs which are clearly and incontrovertibly due to causes other than the study device or study protocol (e.g. concomitant disease, etc)
- Related: AEs which are felt with a reasonable degree of certainty to be related to the study device or study protocol
- Unknown: Adverse events for which a connection with the study device or study protocol cannot be ruled-out with certainty, or not enough information is available to assess the relationship

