## 7.0 CLINICAL ENDPOINTS

### 7.1 SAFETY ENDPOINTS

Safety will be evaluated by assessing the following:

- Percent change in ECC at the 3 Month Visit compared to Preoperative Visit
- Preservation of BCDVA
- SSI
- AE rates as compared to ISO 11979-7:2014 Annex B SPE tables
- Device deficiencies

[figure not shown]

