5.5. Safety analyses

Adverse events and device deficiencies will be summarized at each study visit based on the safety population for Cohort 1 and Cohort 2 separately. The number and percentage of eyes reported with the ISO specified 3-month cumulative and persistent adverse events will be calculated for Cohort 1 and Cohort 2 separately.

Events will be summarized overall for the HMTIOL Cohort 2 and HMIOL Cohort 2. The corresponding one-sided lower 95% confidence limit will be calculated based on the binomial distribution and compared to the ISO SPE rate.

The number and percentage of eyes reported with HMTIOL-related adverse events during the study will be summarized for HMTIOL Cohort 1, HMTIOL Cohort 2, and HMTIOL-eye Cohort. The two-sided 90% confidence interval of the percentage will also be provided.

The number and percentage of eyes reaching BCDVA 20/40 or better, and worse than 20/40 at each visit will be prepared.

[figure not shown]
Rates for adverse events specified in ISO 11979-7:2014 Annex B for posterior chamber IOLs will be summarized at each visit.

Rates of device-related SSIs and device deficiencies will be summarized as described in 5.1 above.

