**8. Interim Analyses**

There are no plans for formal interim analyses for the purposes of study modification or possible early termination. Any interim analyses will be administrative in nature and results will not be distributed to Investigators or subjects to prevent bias from exposure to accruing study results.

SAP CP-00002

[figure not shown]
ClarVista Medical, Inc.

9. Deviations from the Statistical Analysis Plan

Any deviations from the Statistical Analysis Plan will be noted and described with appropriate statistical and clinical rationale as needed. Discrepancies from the Investigational Plan are noted. The primary change is the use of a paired t-test instead of a two-sample t-test to test the primary hypothesis. This change more appropriately accounts for within-patient correlation in ECC. A secondary change was the use of "ECC" rather than "ECL" in Sections 6 and 7 above. ECL is defined in the protocol as follows: "a negative ECC percent change represents an ECC percent loss (ECL)." Since a comparison of 3-month to Pre-operative data may not always result in a measurable loss (e.g., due to measurement error of instrumentation combined with minimal actual ECC loss), ECC is determined to be a more appropriate term.

10. References

1. ISO 11979-7:2014 Ophthalmic implants — Intraocular lenses — Part 7: Clinical investigations.

Alcon - Business Use Only

Document: TDOC-0055985

Status: Effective

Effective Date: 24-Apr-2019

Version: 1.0; CURRENT; Most-Recent; Effective

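### SAP 5.4 and 5.5 narrow the protocol's SSI safety endpoint to device-related SSIs, and SAP Section 9 does not list the change

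*SAP*

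**What the plan says.** The protocol synopsis lists among the safety endpoints "SSI (other than interoperative optic exchange in Cohort 2", closing the bracket there. Protocol 7.1, introduced by "Safety will be evaluated by assessing the following", lists SSI with no qualifier, as one of five items. Neither place makes the endpoint depend on cause.

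SAP 5.4 gives the endpoint as "Rate of device-related Secondary Surgical Interventions (SSIs), other than initial intraoperative exchange for cohort 2". SAP 5.5 carries this into the analysis: "Rates of device-related SSIs and device deficiencies will be summarized as described in 5.1 above".

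SAP Section 2 settles precedence: "Analyses described here supersede those described in the Investigational Plan". SAP Section 9 states "Discrepancies from the Investigational Plan are noted" and then describes two changes: a paired t-test in place of a two-sample t-test, and the term ECC in place of ECL. The SSI endpoint is not among them.

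**The concern.** The SAP keeps the protocol's one exclusion and adds a condition the protocol does not have. A safety rate limited to device-related procedures can only equal or fall below the rate for all procedures, so the change can only make the result look the same or better. Section 9 records even a change of terminology, so a reader of the study report would reasonably take its list as complete and read the SSI rate as the protocol's endpoint.

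The condition also rests on a judgement that the visible text does not fully specify for procedures. Protocol 6.2.1.4 rates adverse events, and its middle level reads "Related: AEs which are felt with a reasonable degree of certainty to be related to the study device or study protocol", so device and protocol share one level. A third level, Unknown, covers events whose connection cannot be ruled out. The SAP does not say on which side of the device-related line an Unknown case falls, or what happens to a procedure that has no adverse event record.

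**Working it through.** The documents give no SSI rate, threshold or sample size, so there is no planned figure to reproduce. The check is a comparison of texts, followed by simple arithmetic on the size of one reclassification.

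**1. The endpoint in the four places where it appears**

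| Place | Exchange in Cohort 2 excluded? | Limited to device-related? |
|---|---|---|
| Protocol synopsis, safety endpoints | Yes | No |
| Protocol 7.1 | Not stated | No |
| SAP 5.4 | Yes | Yes |
| SAP 5.5 | Not restated | Yes |

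Both SAP entries carry the extra condition and neither protocol entry does. Section 2 makes the SAP govern, and Section 9 is silent.

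**2. Can device-relatedness be read from the data for every SSI?**

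- If the reason for surgery is recorded as an adverse event, largely yes. Protocol 6.2.1 has each event classified, with adverse device effect as one class, and 6.2.1.6 links surgical treatment of an event to the Concomitant Procedure form. What remains open is the Unknown level.
- If there is no adverse event record, no rating is described. Protocol 3.3.3 says of postoperative surgery for unacceptable residual refractive error: "The course of treatment will follow the Investigators SOC and be collected as a concomitant procedure". Protocol 4.8.2 requires an indication for each procedure but lets it sit in either Ocular History or the adverse event form. Protocol 6.1.1 keeps stable pre-existing conditions off the adverse event pages, and inclusion criterion 4 means every subject has pre-existing corneal astigmatism in at least one eye. Corneal surgery for residual astigmatism is therefore a possible example of an SSI with no rating.

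**3. Size of one reclassification**

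Inputs: up to 32 subjects, one eye per cohort (Protocol 3.1), so at most 32 eyes per cohort and 64 in all. With x eyes classed out of n, the reported rate falls by x/n.

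- One eye in a cohort: 1/32 = 3.125%, about 3.1 points.
- Two eyes in a cohort: 2/32 = 6.25%, about 6.3 points.
- One eye, both cohorts pooled: 1/64 = 1.5625%, about 1.6 points.
- One eye, if a cohort had only the 25 eyes that SAP Section 6 requires for the ECC comparison: 1/25 = 4.0 points.

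The documents give no expected count, so x is an assumption. For x from 0 to 2 in a full cohort, the shortfall runs from 0 to 6.3 points.

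**The case against.** Four arguments stand against making more of this.

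- **An all-SSI rate may exist elsewhere.** A reader might infer that the protocol's own rate will never be produced. The documents do not establish that. SAP 5.5 also summarises the adverse event rates specified in ISO 11979-7:2014 Annex B, with no device-related filter, and whether that list covers SSIs cannot be checked from these documents. In addition, a figure is not shown in SAP 5.5 and SAP 5.7 appears as a heading without visible text. This stands, and it limits the point to the SSI endpoint and rate named in 5.4 and 5.5.
- **Most SSIs would probably be rated.** A reader might infer that refractive surgery will routinely escape classification. The documents point the other way. Protocol 6.1.2 defines an adverse device effect by its causal link to use of the device, 6.2 gives explantation for component damage as an example, and 6.3.1 requires expedited reporting of device-related events and of HMIOL explants. Protocol 3.3.3 treats unacceptable refractive error as a postoperative outcome, and Appendix A schedules history only at the preoperative and operative visits. The unrated procedure is thus a narrow and contestable case. Even with every SSI rated, however, the named rate would still leave out those not classed as device-related.
- **The protocol's 6.7% figure does not measure the loss.** A reader might use the SSI rate in Protocol 1.0 to estimate how many eyes would drop out. That figure is for repositioning of another toric lens, a kind of SSI likely to be called device-related, so it says little about SSIs that would be excluded.
- **The consequences are limited.** This is a feasibility study. Adverse events and device deficiencies are summarised whatever their cause, and procedures are captured on the eCRF. This stands, and it keeps the point modest.

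**Conclusion.** The point holds as an unlisted narrowing of a safety endpoint. The superseding SAP limits the named SSI endpoint and its rate to device-related SSIs, the protocol does not, and Section 9 does not record the difference. How Unknown or unrated cases are classed is not visible.

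The effect is confined to the reported SSI rate: 3.1 points for each eye classed out of a full 32-eye cohort, and somewhat more with fewer eyes. This assumes the enrolment ceiling is reached. It does not predict that any eye will be classed out. No data are lost, and the visible text ties no test, threshold, power or sample size to this rate. Confidence limits are left out because SAP 5.1, to which 5.5 refers for SSIs, plans only counts and percentages for categorical measures. The change is worth making because it is cheap and the endpoint concerns safety.

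**What to change.** In SAP 5.4 and 5.5, report the number and percentage of eyes with any SSI other than the planned Cohort 2 exchange, by cohort, identified from the Concomitant Procedure eCRF. Below that, show device-related SSIs as a subset, with Unknown or unrated cases on their own line. Because the form also takes non-invasive procedures (Protocol 4.8.2), add a sentence saying which entries count as an SSI.

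If the sponsor prefers to keep the narrower endpoint, list it in SAP Section 9 with a justification and state the rule for Unknown and unrated cases.

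The cost is a change of wording and a few table rows from data already collected. The downside is that the SSI rate may read higher.
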